1.1 Objectives/Hypotheses

Promoting Follow-Up Care Self-Management for Adolescent and Young Adult (AYA) Childhood Cancer Survivors

[name], MPH

Aim 1: Adapt PSST with peer mentoring to improve AYA self-management of long-term follow-up care.

Qualitative research with AYA cancer survivors, parents, and healthcare providers will be conducted to adapt an evidence-based problem-solving skills training (PSST) program to address the needs of AYA survivors.

Aim 2: Evaluate the feasibility of the self-management + peer mentoring program in a pilot RCT.

We will examine feasibility through study enrollment rates, retention rates, adherence to the intervention, reasons for study drop out, and patient and mentor satisfaction with the program.

Hypothesis 1: Based on literature, we expect enrollment >50% of eligible patients and retention >75%.

Hypothesis 2: We expect patients enrolled in the mentor program to complete >75% of intervention sessions

Aim 3: Assess preliminary outcomes of the peer mentoring program.

Hypothesis 3: Participants in the mentor group will demonstrate improvement in self-management skills, transition readiness, and anxiety.

2. Background and Significance

The transition to adult self-management of health care is often ineffectively managed by AYAs.

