Phase 2: Peer mentors will be recruited via advertisements in the CINJ LITE clinic and newsletter, AYA cancer support groups, and online forums/social media, such as stupidcancer.org. Following the Children's Oncology Group's approach to recruiting patient advocates, potential mentors will complete an application including two letters of recommendation. The PI or study staff will interview candidates to evaluate interpersonal skills, level of commitment to the program, and counseling or related experience. Participants for the randomized trial will be recruited using the New Jersey State Cancer Registry (NJSCR). All participant information and surveillance data from the NJSCR is collected and maintained by the NJSCR following Standard Operating Procedures (see IRB#Pro20140000992 NJSCR SEER Data Repository). Patient contact procedures, tracking, and data release also follows NJSCR Standard Operating Procedures. Per Standard Operating Procedures, NJSCR staff will contact the physician of record for eligible cases to notify the physician about the study and that staff will be contacting the patient. An introductory letter and flyer will be mailed to potential participants. NJSCR staff will make follow-up phone calls to provide additional information and, for patients who express interest in participating, to obtain permission

Promoting Follow-Up Care Self-Management for Adolescent and Young Adult (AYA) Childhood Cancer Survivors

[name], MPH

to send their contact information to [name] study staff, who will then contact the patient for further details and discussion of consent.

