Satisfaction with Intervention. At the 6 week post-intervention assessment, participants will be asked to complete a survey regarding their satisfaction with the intervention received and recommendations for improvement. For the intervention group receiving the online modules and peer mentor, items from a standardized set of internet-based intervention evaluation tools will be used - Internet Intervention Utility Questionnaire, Impact Questionnaire, and Adherence Questionnaire.^{36,37} The Utility Questionnaire measures perceived usefulness, enjoyment, and ease of use. The Impact Questionnaire measures perceived effectiveness in improving targeted skills. The Adherence Questionnaire measures barriers to engagement. Objective user data (i.e., log-ins, posts, modules completed) will be obtained unobtrusively from Canvas. Peer mentors will be given an interview (i.e., Peer Mentor Interview) at the end of the program to assess their thoughts about the program (what went well, did not work well, etc.) The participants will also be asked to do a brief (~20 minute) phone exit interview with the PI or the study staff to gather qualitative feedback on how to improve the program in the future (see Participant Exit Interview Guide).

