4.4 Potential for Benefit

Phase 1: There is no direct benefit to participants.

Phase 2: There may or may not be a direct benefit to participants. All participants will receive information regarding self-management that may be useful to participants but the study will

Promoting Follow-Up Care Self-Management for Adolescent and Young Adult (AYA) Childhood Cancer Survivors

[name], MPH

evaluate the feasibility of implementing the interventions as well as participant-reported satisfaction and relevant quality of life outcomes.

5. Data Handling and Statistical Analysis

Phase 1 (Aim 1):

Data Management: Digital recordings will be transferred off of the recorders to the PI's secure shared drive as soon as possible following the interview and then erased from the recorder. Transcription will be completed as soon as possible, removing any identifiable information. All transcriptions will be labeled with a subject number rather than any identifiable information. Digital recordings will be deleted after they are described and checked for accuracy. Paper questionnaires will be labeled with an ID number and stored separately from consent forms in a locked cabinet in the PI's locked office. The key linking subject names and subject numbers will be stored electronically on the PI's password-protected CINJ internal shared drive and destroyed at the end of the study.

Data Analysis: Qualitative data will be analyzed using content analysis, following the framework approach described by Pope and colleagues.³⁸ Specifically, themes will be identified based on the a priori theoretical framework (SMART model). Data will be constantly compared to evaluate fit to the model and new themes that emerge from participants' data will be added to the model. An index of themes will be created and applied systematically to the data using NVivo, a qualitative data analysis software. Data analysis will continue until theme saturation occurred (that is, no new themes emerge from additional participants). Participant feedback on questionnaires will be used to determine if any changes are needed to the outcome measures for Phase 2 of the study.

Phase 2 (Aims 2 & 3):

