To assess the preliminary outcomes of the peer mentor self-management program, we will evaluate whether participants in the program demonstrate improvement in transition readiness and the impact of cancer, and reductions in symptoms of depression and anxiety. We will also explore adherence outcomes. We will compare scores on outcome measures at the end of 6-week assessment using dependent/paired t-tests. Since the primary purpose of this project is to evaluate feasibility, we recognize that we do not have adequate power to detect small to medium statistical effects. Exit interviews will be reviewed to identify strengths of the intervention, weaknesses of the intervention, and ideas to improve the intervention.

6. Data and Safety Monitoring

This study is minimal risk. The PI and co-investigators will monitor for adverse events and report any events according to RBHS IRB guidelines.

7. Reporting Results

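### Phase 2 is labelled a randomised trial, but no comparator, allocation or arm sizes are defined, and the paired t-tests named for Aim 3 cannot estimate a randomised effect; one design must be stated

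*Combined protocol and SAP*

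**What the plan says.** Several places treat Phase 2 as randomised or as having more than one group:

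- Section 1.1, Aim 2: "Evaluate the feasibility of the self-management + peer mentoring program in a pilot RCT".
- Section 3.5.3: "Participants for the randomized trial will be recruited using the New Jersey State Cancer Registry (NJSCR").
- Section 1.1, Hypothesis 3: "Participants in the mentor group will demonstrate improvement in self-management skills, transition readiness, and anxiety".
- Section 4.2, on satisfaction, assigns a set of internet-intervention questionnaires as follows: "For the intervention group receiving the online modules and peer mentor". The same paragraph asks participants to "complete a survey regarding their satisfaction with the intervention received and recommendations for improvement".
- Section 4.4: "All participants will receive information regarding self-management that may be useful to participants", and the study will "evaluate the feasibility of implementing the interventions as well as participant-reported satisfaction", with interventions in the plural.

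Other places describe a single program given to a single group. Sections 1 and 3 speak of a pilot test of the program in 40 survivors. Section 3.1 asks participants to complete the six-week intervention. Section 4.1 describes one intervention (online modules plus mentor calls), says participants are matched with a mentor, and lists the Phase 2 independent variables without a treatment arm. Section 3.3 gives 40 survivors and 20 mentors with no split.

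Section 4.2 schedules the measures at baseline and at about six weeks. For Aim 3, Section 5 asks whether program participants improve, and names one method: "We will compare scores on outcome measures at the end of 6-week assessment using dependent/paired t-tests". It specifies no between-group comparison.

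**The concern.** The design label and the analysis do not belong to the same study. A randomised trial is run to obtain a contrast between arms, and here no planned analysis uses one. A single-arm study can be analysed with paired tests, but then it is not an RCT. Section 1 describes the change in survivors' scores as preliminary efficacy. Without a comparison group that change mixes any program effect with whatever would have happened over six weeks anyway. Published under an RCT label, it could be read as randomised evidence.

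The ambiguity also reaches the primary aim. Hypothesis 2 on session completion is confined to patients in the mentor program, and the Section 4.2 questionnaires are confined to the intervention group. Whether those groups contain all 40 survivors or only some of them is not stated.

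**Working it through.** **1. Can the design be recovered from the text?** The wording quoted from Section 4.2 is the strongest sign of a second arm: giving specific questionnaires to one named group implies another. It does not say what the other group receives. The plural in Section 4.4 and the reference to the intervention received are weaker hints of the same kind. Against this stand the single program in Sections 1, 3, 3.1 and 4.1 and the absence of an arm variable in Section 4.1. The 20 mentors do not fix arm sizes, since Section 3.5.5 pays mentors per participant mentored. The text does not settle the design.

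**2. Can it be recovered from the sample size?** The figure of 40 cannot be reproduced: the documents give no alpha, power, effect size, SD or allocation ratio. The only power statement (Sections 3.3 and 5) is that power is inadequate for small to medium effects. I checked it under each design.

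Inputs: 40 survivors (Section 3.3); 0.75 × 40 = 30 retained, the floor of the retention benchmark (Sections 1.1 and 5). Assumed: two-sided alpha 0.05, 1:1 allocation if two arms, standardised effect 0.5.

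Formula: power = P(|T| > t at 0.975), T noncentral t. Paired: noncentrality dz × √n, n − 1 df. Two arms of n: noncentrality d × √(n/2), 2n − 2 df.

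| Design | Noncentrality at 0.5 | Power |
|---|---|---|
| Paired, n = 40 | 0.5 × √40 = 3.16 | 0.87 |
| Paired, n = 30 | 0.5 × √30 = 2.74 | 0.75 |
| 20 v 20 | 0.5 × √10 = 1.58 | 0.34 |
| 15 v 15 | 0.5 × √7.5 = 1.37 | 0.26 |

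Here dz is in SDs of the difference. If 0.5 is in raw score SDs, dz = 0.5/√(2(1 − r)), and paired power at n = 40 runs from 0.74 to 0.98 for an assumed baseline-to-6-week correlation r of 0.3 to 0.7. The power statement fits two arms better, while the named test fits one group. The sample-size section does not settle the design either.

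**3. What could a between-arm comparison detect?** Solving the two-arm formula for 80% power, unadjusted, gives d = 0.91 at 20 v 20 and d = 1.06 at 15 v 15. Adjusting for baseline multiplies the SD by √(1 − r²). At r = 0.3 / 0.5 / 0.7 the formula gives 0.87 / 0.79 / 0.65 at 20 v 20 and 1.01 / 0.92 / 0.76 at 15 v 15. It ignores chance baseline imbalance, and simulated power at these values is about 78–79%.

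**4. What does the design do to precision?** 95% CI half-widths in score SDs, at 75% retention:

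- Paired change, n = 30: t(29) × √(2(1 − r)/30). At r = 0.5, 2.045 × 0.1826 = 0.37; at r = 0.3 and 0.7, 0.44 and 0.29.
- Adjusted difference, 15 v 15: t(27) × √(2/15) × √(1 − r²). At r = 0.5, 2.052 × 0.3651 × 0.866 = 0.65; at r = 0.3 and 0.7, 0.71 and 0.54.

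These are different estimands. The comparison shows the price of a controlled answer, not that one method is better at the same task.

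**5. Feasibility denominators.** If all 40 are mentored, session completion is estimated in 40. At an assumed 1:1 it is estimated in 20, and its standard error is √(40/20) = 1.41 times as large for the same between-person spread.

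**The case against.** The strongest defence is that this is a feasibility pilot. Aim 3 is secondary, the plan twice disclaims power, and Section 5 makes no causal or between-group claim. Most of the operative text reads as a single-arm study, in which case the repair is to wording alone. Hypothesis 3 asks whether the mentor group improves, and a paired test answers that, either in a single-arm study or within one arm of an RCT.

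Much of this stands. A reader might infer that paired tests are invalid here or can fit only a single-arm design; neither follows. What remains is that they do not estimate a randomised effect or attribute change to the program. The single-arm reading cannot be taken as settled either, given the randomised wording in Sections 1.1 and 3.5.3 and the questionnaires reserved for an intervention group in Section 4.2.

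A reader might also assume some background improvement and present the resulting paired-test rejections as false positives. The documents give no source for such a drift. If it is real, rejecting no change is correct; the error arises only when a causal claim is added.

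Finally, a reader might suspect bias because low readiness on the Readiness for Transition Questionnaire (RTQ) is an eligibility criterion (Section 3.5.1) and the RTQ is also an outcome. Section 4.2 schedules a baseline administration, and nothing says the screening score will replace it. In a randomised, baseline-adjusted analysis, regression to the mean acts on both arms alike; simulation with the screening score as baseline kept the rejection rate at about 5%. The point is advisory and applies only to single-arm change.

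**Conclusion.** The plan is wrong as written on this point: under either design, some text must change. The contradiction rests on the documents alone and needs no assumed figure. It bears directly on secondary Aim 3 and, through the denominators for session completion and program satisfaction, on part of the primary feasibility aim. The descriptive approach to feasibility is not itself at fault.

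The documents do not show which design was intended, so neither a concealed control arm nor a purely mistaken label should be inferred. The detectable effects of 0.91 (20 v 20) and 1.06 (15 v 15) are illustrations that rest on assumed 1:1 allocation, two-sided alpha 0.05 and 80% power without adjustment. They show that a randomised comparison of this size could detect only large effects, which is consistent with the plan's own disclaimer.

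**What to change.** Reconcile Sections 1, 1.1, 3, 3.1, 3.3, 3.5.3, 4.1, 4.2, 4.4 and 5 to one design.

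*If randomised:* state the comparator, the allocation and the arm sizes. Make the Aim 3 analysis a baseline-adjusted between-arm difference at 6 weeks with a 95% CI, analysed as assigned (ANCOVA, for example). Keep within-arm change as description only. State that session completion and mentor-program satisfaction are estimated in the mentored arm.

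*If single-arm:* remove the RCT, randomized-trial and intervention-group wording. Report mean change with a 95% CI, and state that it is uncontrolled and not evidence of a program effect. As advice for this case only, do not use the RTQ screening score as the baseline, since selection on a low score can produce an apparent rise; the documents do not allow its size to be estimated.

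*Cost:* the single-arm repair is wording, at the price of a weaker efficacy statement. The randomised repair requires the comparator and allocation to be written in and one model to replace the t-tests; the total of 40 need not change. Its price is a wider interval for Aim 3 and the loss of precision from estimating session completion and mentor-program satisfaction in only part of the 40.

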7.1 Individual Results

N/A

7.2 Aggregate Results

Aggregate results will be reported in scientific publications. Plain language summaries will also be made available at the end of the study. After participants complete the final assessment, we will have a separate form that they can voluntarily complete with preferred contact information (i.e., mail, email) to receive a summary of aggregate results. This information will be stored confidentially until the summary is provided, at which time the contact information will be destroyed.

